 - Alcohol consumption: life time alcohol consumption and consumption within the year prior to the liver biopsy.
 - Viral factors: HCV genotype, HCV RNA level.
 - Hepatic inflammation: ALT level and hepatic inflammation grade.
 - Iron: serum iron, TIBC and hepatic iron score.

Risk factor data such as BMI, life time alcohol consumption, diabetes status etc. will be coded as categorical or continuous variables as appropriate. These will be evaluated against the degree of steatosis (5 levels) and dichotomous collapsed steatosis codes (such as <33% vs \geq 33%) using the Cochran-Mantel-Haenszel chi-square test with one degree of freedom. Multivariate analysis will be performed using logistic regression analysis. These risk factor variables and the steatosis levels will similarly be evaluated against the fibrosis scores (6 levels). Because fibrosis will also be quantified morphometrically, it will also be analyzed as a dependent variable by analysis of variance.

4. These risk factors and their relationship to week 20 and sustained virologic response will also be assessed.

Univariate analysis will be carried out using categorical or continuous variables as appropriate. These will be categorized against dichotomous (W20 responder v nonresponder, SVR v no SVR (all W20 nonresponders will be categorized as no SVR)) variables using the Cochran-Mantel-Haenszel chi-square test with one degree of freedom. Multivariate analysis will be performed on significant variables identified in univariate analysis by logistic regression.

Longitudinal study

The following analyses will be performed:

1. Prevalence of hepatic steatosis in year 4 biopsies will be compared to the year 2 and baseline biopsies of all patients and separately for the treated patients and controls.
2. Changes in hepatic steatosis between year 4 and baseline biopsies will be compared for the entire cohort of patients, and separately for the treated patients and controls.
3. Correlation between changes in hepatic steatosis with changes in hepatic fibrosis.
4. Correlation between changes in hepatic steatosis and changes in other risk factors for hepatic steatosis such as BMI, alcohol consumption, triglyceride level, hepatic inflammation, and hepatic iron content.
5. Correlation between changes in insulin resistance (measured using the homeostasis model assessment (HOMA)) from baseline to week 60 of the lead-in patients and virologic response or relapse.

We will compare HOMA-IR (calculated from fasting insulin and glucose levels) from subjects at entry into the lead in phase of HALT-C and compare week 60 samples from among responders (HCV RNA undetectable) and relapsers (HCV RNA +). Because of inherent insulin resistance among diabetic patients, we will confine the analysis to nondiabetic subjects (about 80%) of those with W60 samples. This would comprise about 250 subjects with available W60 sera. These would be evenly divided between responders and relapsers (125 in each group). Changes in HOMA-IR would be calculated between the responder and relapser groups. An advantage of studying W60 sera is that any confounding effects of PEGIFN and RBV on IR will be minimized, including weight loss on therapy. If differences can be discerned between the 2 groups, then it will also be of interest to perform W20 determinations among responders and nonresponders in a larger number of subjects. A secondary analysis would include assessment of the correlation between HOMA-IR and HCV RNA levels at baseline for all subjects and at W60 for relapsers, as well as correlation of virologic response or relapse with fasting glucose levels and HgbA1c in those persons with diabetes or impaired glucose tolerance (about 20% of the group).

PITFALLS AND LIMITATIONS

This study does not involve any additional invasive tests or time commitment from the trial participants. Most of the data required will be collected as part of the main trial, so we do not anticipate there will be any problem in conducting this study. It is possible that steatosis may have no role in the development of fibrosis/cirrhosis in patients with chronic hepatitis C. However, results from studies in patients with NASH and the recent report of Hourigan support that steatosis may be important in hepatic fibrogenesis. Patients in this study will all have significant fibrosis (Ishak score ≥ 3) and non-response to prior interferon therapy. Results of our study may not necessarily apply to other patients with chronic hepatitis C. However, the patients we will be studying are at greatest risks of developing fibrosis and cirrhosis, and any factor that can promote fibrosis should be easily demonstrated in this study.

REFERENCES

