Hepatic Steatosis Snap Shot

Sites Participating: All sites

Principal Investigator: [name] (University of Michigan)

Co-Investigators: [name]; [name]; [name];
[name]

Study Name: HEPATIC STEATOSIS IN CHRONIC HEPATITIS C: RISK FACTORS AND ROLE ON THE DEVELOPMENT OF HEPATIC FIBROSIS

Separate Consent Form: No

Withdrawal Form: No

Eligible Patients: Lead-in, Randomized, W20 Responders, Sustained Virologic responders and Breakthrough/Relapser
(Express patients are not eligible)

Visit Schedule (additional data/specimen and forms for AS)

Note: "X" means all participating sites take part.

Lead-In Phase

Visit Number →	Form #	S00	W00	W02	W04	W08	W12	W16	W20	W24
Fasting Insulin seq.121	Excel file		X							
Glycosylated Hemoglobin	121	X								

Randomized Phase

Visit Number →	Form #	R00	M12	M18	M24	M30	M36	M42	M48	M54
Fasting Insulin seq. 121	Excel file				X					
Glycosylated Hemoglobin	121									

Hepatic Steatosis in Chronic Hepatitis C: Risk factors and role in the development of hepatic fibrosis

Principal Investigator: [name]

Co-Investigators: [name], [name], [name], [name]

SPECIFIC AIMS:

The central hypothesis of this ancillary study is that hepatic steatosis plays a key role in the development of fibrosis and cirrhosis in patients with chronic hepatitis C. In addition, we hypothesize that both viral and non-viral factors are involved in the development of hepatic steatosis in patients with chronic hepatitis C, and the benefits of long-term interferon therapy is in part mediated via reduction of hepatic steatosis. The specific aims of this study are:

1. To determine the prevalence of hepatic steatosis in patients with chronic hepatitis C.
2. To determine if there is a correlation between hepatic steatosis and hepatic fibrosis in patients with chronic hepatitis C.
3. To identify viral and non-viral risk factors for hepatic steatosis in patients with chronic hepatitis C.
4. To identify metabolic predictors of week 20 and sustained virologic response
5. To determine the effects of long-term interferon therapy on hepatic steatosis in patients with chronic hepatitis C.
6. To determine the effects of virologic clearance on insulin resistance in patients with chronic hepatitis C.

RELATIONSHIP OF PROPOSED STUDY TO NIH HALT-C TRIAL

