This ancillary study will examine the prevalence and severity of hepatic steatosis in a large cohort of patients with chronic hepatitis C. Viral and non-viral risk factors for hepatic steatosis will be assessed prospectively. Hepatic steatosis will be graded using a standardized scoring system and will be correlated to semi-quantitative (Ishak) and quantitative (morphometry) assessment of hepatic fibrosis. The effects of interferon therapy on hepatic steatosis will also be determined. The advantages of utilizing the HALT-C trial for our proposed ancillary study include the large sample size, long duration of follow-up and the inclusion of an untreated control group. Because this is a prospective study, alcohol consumption can be more reliably assessed. Detailed and accurate quantification of past and current alcohol consumption is a major focus of the HALT-C trial. Life-time and ongoing alcohol consumption will be determined using the Skinner survey. Other risk factors that have not been examined in previous studies such as fat distribution and hyperinsulinemia will be evaluated. This trial will enable us to examine the prevalence and impact of hepatic steatosis in patients with chronic hepatitis C both cross-sectionally and longitudinally. The longitudinal part of the study will allow us to determine if hepatic steatosis in patients with hepatitis C fluctuate over time and to identify factors that correlate with these changes. It will also determine if changes in hepatic steatosis correlate with changes in hepatic fibrosis further supporting a role of hepatic steatosis in fibrogenesis. Long-term interferon therapy can potentially decrease steatosis by inducing weight loss or increase steatosis by elevating serum triglyceride level. This study will determine the net effects of long-term interferon therapy on hepatic steatosis in patients with chronic hepatitis C.

MATERIALS AND METHODS

Inclusion/Exclusion:

All Lead-in patients enrolled in the NIH HALT-C trial will be studied. This study will enroll approximately 1000 patients with chronic hepatitis C who have significant fibrosis (Ishak score of 3-6). Patients with other causes of liver disease will be excluded from this study. Express patients are not eligible for the Steatosis Ancillary Study.

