Patients will receive 6 months of combination therapy of interferon and ribavirin during the lead-in phase. Patients who remain viremic at treatment week 20 will be eligible for continued participation in this trial. These patients will be randomized to continue treatment with interferon alone for 3.5 years or no treatment. All patients will have repeat liver biopsies at the end of years 2 and 4.

This ancillary study will consist of a **cross-sectional** and a **longitudinal part**. In the following pages:

◆ Indicates additional data/sample collection for this ancillary study.

Schedule of Visits and Specimen Collection:

Cross-sectional Study – All tests performed at Screening (S00) or Baseline (W00).

This study will include all patients who remain eligible for continued participation in the NIH HALT-C trial after the lead-in phase. Baseline clinical data will be collected for all enrolled patients. Tests for insulin level and grading of liver biopsies for hepatic steatosis will not be performed until all patients have completed the lead-in phase to determine who will remain in the trial.

During the screening phase, clinical data will be collected and blood tests will be performed as part of the main protocol. Fasting blood glucose and triglyceride levels will be checked. Patients with known diabetes will be tested for glycosylated hemoglobin (HbA1c). These procedures are part of standard care of hepatitis C patients evaluated for interferon treatment and will be performed as part of the main protocol. An additional sample of blood will be collected for insulin level. Baseline liver biopsies will be scored for inflammation, fibrosis and iron. These assessments will be performed as part of the main protocol. The biopsies will additionally be graded for hepatic steatosis.

Baseline clinical data will be collected during the screenings or at baseline on:

- a) Sex, age, ethnicity, Form #1, Trial ID Assignment.
- b) Total body fat estimated by body mass index (BMI). BMI will be derived from body height and weight, Form #11, Physical Exam.
- c) ♦ Visceral fat estimated by waist circumference taken with a cloth tape at the level of the umbilicus, with the patient supine, Form #11, Physical Exam (See Appendix A for directions).
- d) Quantitative lifetime alcohol consumption and alcohol consumption during the year prior to entry into the Trial based on Skinner survey, Form #41.

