- e) ♦ History of diabetes, Form #3, Screening Medical History Interview. Current use of diabetic medications, Form #3, Screening Medical History Interview, and Form # 7, Baseline Medications Interview.
- f) History of hyperlipidemia, Form #3, Screening Medical History Interview. Current use of lipid lowering medications, Form #3, Screening Medical History Interview, and Form #7, Baseline Medications Interview.
- g) ♦ History of morbid obesity, Form #3, Screening Medical History Interview and Form #146, Weight History. Previous treatment for obesity such as jejunoileal bypass, Form #3, Screening Medical History Interview.
- h) ♦ Concomitant medications that may induce hepatic steatosis, Form #7, Baseline Medications Interview.

Laboratory tests during the screening phase (S00):

- a) Liver panel including AST and ALT, Form #35, Screening Visit 2 Local Lab.
- b) HCV genotype, Form #33, Central Lab - HCV Genotype.
- c) HCV RNA level, Form #31, Central Lab – HCV RNA.

- d) Serum iron/TIBC, Form #30, Local Lab.
- e) ♦ Fasting blood glucose, Form #30, Local Lab, and HbA1c for known diabetics, Form #121, Glycosylated Hemoglobin.
- f) Fasting triglyceride, Form #30, Local Lab.
- g) ♦ Fasting insulin level during the baseline visit (W00). Fasting insulin level will be tested at the Michigan Diabetes Center. Fasting insulin results will be sent to NERI as an excel file.

Baseline liver biopsies will be assessed by the central Pathology Committee for:

- a) Hepatic inflammation according to Ishak score.
- b) Hepatic fibrosis according to Ishack score as well as computerized morphometry after staining with sirrus red.
- c) Hepatic iron content according to the method determined by the Pathology Committee.
- d) ♦ Hepatic steatosis – the same H&E slide used for grading hepatic inflammation will be used to quantify hepatic steatosis. Hepatic steatosis will be scored based on percent of hepatocytes with fat. Scores will range from 0 to 4+: 0 (none), 1+ (1-5%), 2+ (5-33%), 3+ (33-67%), and 4+ (>67%).

Longitudinal study: This study will include all patients who completed the trial and have repeat liver biopsies at the end of years 2 and 4.

Serial clinical data will be collected on:

- a) Body weight at each visit, Form #11, Physical Exam. This will permit changes in total body fat or BMI to be determined.
- b) ♦ Waist circumference will be determined at the end of year 2 (M24) and 4 (M48) to assess changes in visceral fat, Form #11, Physical Exam.

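### The longitudinal steatosis analyses specify no treated-versus-control contrast, so as written they do not estimate the effect of long-term interferon (Aim 5)

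*Combined protocol and SAP*

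**What the plan says.** SPECIFIC AIMS, aim 5: "To determine the effects of long-term interferon therapy on hepatic steatosis in patients with chronic hepatitis C".

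MATERIALS AND METHODS, Inclusion/Exclusion, on patients still viremic at week 20: "These patients will be randomized to continue treatment with interferon alone for 3.5 years or no treatment". All of them have first had 6 months of interferon plus ribavirin.

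BACKGROUND AND SIGNIFICANCE lists among the advantages of using this trial the "long duration of follow-up and the inclusion of an untreated control group", and states: "This study will determine the net effects of long-term interferon therapy on hepatic steatosis in patients with chronic hepatitis C".

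Two items under DATA ANALYSES, Longitudinal study, bear on this aim:

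- Item 1: year 4 prevalence "will be compared to the year 2 and baseline biopsies of all patients and separately for the treated patients and controls".
- Item 2: changes between the year 4 and baseline biopsies "will be compared for the entire cohort of patients, and separately for the treated patients and controls".

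Items 3 and 4 correlate changes in steatosis with changes in fibrosis and in risk factors, without reference to arm. Item 5 concerns insulin resistance by virologic response. The methods the plan names (Cochran-Mantel-Haenszel, logistic regression, analysis of variance) are in the cross-sectional part, where randomized arm is not a listed factor.

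The longitudinal analysis set is defined under MATERIALS AND METHODS, Longitudinal study: "This study will include all patients who completed the trial and have repeat liver biopsies at the end of years 2 and 4".

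**The concern.** Of the six aims, Aim 5 is the one that depends on the randomization. The plan itself says that interferon might lower steatosis through weight loss or raise it through triglycerides, so a net effect has to be measured against concurrent untreated patients. What items 1 and 2 would deliver is a pooled change and two within-arm changes, with no estimate of the difference between arms and no measure of its uncertainty.

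Within-arm change from baseline is not a substitute. Baseline biopsies belong to screening or week 0, before the combination lead-in. Any steatosis change caused by the lead-in, and any drift over four years, appears in both arms and would be credited to or set against interferon. The result could be an apparent effect that is not there, or a real one that is missed. The hypothesis that interferon's benefit runs partly through reduced steatosis also draws on this answer.

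**Working it through.** The plan gives no sample size, power, alpha or effect size for Aim 5, so it has no figure to reproduce. The check has three steps.

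**1. What each planned quantity estimates.** Write L for the lead-in effect on steatosis, T for the time trend and I for the effect of randomized interferon, all from baseline to year 4.

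- Treated arm, year 4 minus baseline: L + T + I
- Control arm, year 4 minus baseline: L + T
- Whole cohort, assuming 1:1 allocation: L + T + I/2
- Treated minus control: (L + T + I) − (L + T) = I

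Only the last line isolates I, and it is the one not specified. Item 1 also compares year 4 with year 2. That interval starts after the lead-in, but within an arm it still contains the time trend, and it leaves out any interferon effect already present at year 2.

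**2. Illustration of arm-by-arm reading.** Assumptions not in the documents: two-sided 5% tests within each arm, the same true change in both arms (I = 0), and within-arm power p. The arms are independent, so

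P(exactly one arm significant) = 2p(1 − p).

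| Within-arm power p | 2p(1 − p) |
|---|---|
| 0.05 (no change in either arm) | 2 × 0.05 × 0.95 = 0.095 |
| 0.20 | 2 × 0.20 × 0.80 = 0.32 |
| 0.50 | 2 × 0.50 × 0.50 = 0.50 |
| 0.80 | 2 × 0.80 × 0.20 = 0.32 |
| 0.90 | 2 × 0.90 × 0.10 = 0.18 |

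Half of each figure is the treated arm alone reaching significance, and half is the control arm alone.

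For a size, DATA ANALYSES says the study will have 3-4 times the patients of an earlier 148-patient study. Taken as a multiple, 3 × 148 = 444 and 4 × 148 = 592, or 222 and 296 per arm at 1:1. Simulation at those sizes (8,000 runs, normally distributed changes) gave one-arm-only significance in 0.100 and 0.095 of runs with no change, 0.496 and 0.503 at about 50% power, and 0.312 and 0.316 at about 80% power. A direct between-arm test rejected in 0.048 to 0.054 of the same runs.

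**3. Whether the direct comparison is worth making.** The detectable difference at 80% power is (1.960 + 0.842) × √(2/n) in SD units of change.

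- n = 222: 2.802 × √(2/222) = 0.27 SD
- n = 296: 2.802 × √(2/296) = 0.23 SD
- If only 70% have paired biopsies (an assumption): n = 155 gives 0.32 SD and n = 207 gives 0.28 SD

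For year 4 prevalence, take control values of 31%, 50% or 72% (31% and 72% are the ends of the range the plan quotes) and a lower value in the treated arm:

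| Difference in prevalence | Power, 222 per arm | Power, 296 per arm |
|---|---|---|
| 10 points | 56-67% | 69-79% |
| 15 points | 90-96% | 96-99% |

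Under these assumptions the trial can detect a moderate arm difference.

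**The case against.** The strongest defence is that the contrast was intended and the text is merely brief. Item 2 already works with within-patient changes and says these will be compared, and the Background names the control group as an advantage and promises net effects. Controls are also reported, so a reader could subtract one arm's change from the other's.

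Part of this stands. A reader might infer that the sponsor decided against a randomized comparison, or that the control group goes unused. The documents support neither: the contrast is unspecified, not ruled out, and both items present controls. But item 2's comparison also covers the entire cohort, where there is no second group, so its natural sense is comparison over time, repeated in each arm. Where the plan wants groups contrasted, it says so, as with responders and relapsers for HOMA-IR and week 20 responders and nonresponders. Subtracting by hand gives a point difference with no planned interval, and only among completers.

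A reader might also infer that the plan would judge interferon by whether one arm is significant and the other is not. No such rule appears; items 1 and 2 name no test or alpha. The probabilities above describe a risk of later misreading. They depend heavily on p, and a near-null common change (the 9.5% row) is plausible: in the one interferon report the plan cites, the proportion with steatosis was unchanged after 6 months of monotherapy.

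Regression to the mean is another tempting addition. The documents do not support it, because patients are selected on fibrosis and prior non-response, not on steatosis grade.

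Finally, Aim 5 is one of six aims of an ancillary study whose main goal is the role of steatosis in fibrosis, and no data collection is affected. That limits the consequences, but the stated analyses still do not answer the stated aim.

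**Conclusion.** The point holds as a gap in specification with a substantive consequence. Followed as written, items 1 and 2 produce pooled and within-arm changes and do not estimate the effect of long-term interferon. The main reason rests on the documents alone: everyone in the lead-in receives the same combination therapy after the baseline biopsy, so change from baseline in either arm, or in both together, carries more than the randomized treatment.

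The size of the resulting error cannot be derived from the documents. The range of 9.5% to 50%, against about 5% for a direct test, is illustrative. It assumes two-sided 5% tests, equal true change in both arms and arm-by-arm reading of significance. The detectable differences of 0.23 to 0.32 SD further assume 1:1 allocation, 444 to 592 patients and 70-100% with paired biopsies.

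**What to change.** Before the follow-up steatosis grades are analysed, add to the Longitudinal study section:

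1. **Aim 5 analysis.** The treated-versus-control difference in follow-up steatosis grade, by randomized assignment and adjusted for baseline grade, with an effect estimate and 95% CI. Suitable choices include a proportional-odds model, a repeated-measures ordinal model using years 2 and 4 with arm, visit and arm-by-visit terms, or a Cochran-Mantel-Haenszel test stratified by baseline grade and accompanied by an effect estimate. Name one in advance.
2. **Analysis set.** All randomized patients with a baseline and at least one follow-up biopsy, in place of completers with both. Comparing arms among completers alone would not preserve the randomization if drop-out differs by arm.
3. **Missing biopsies.** A sensitivity analysis, with the number and timing of missing biopsies reported by arm.
4. **Within-arm and pooled changes.** Keep them as description only.

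The cost is SAP wording and a modest amount of extra analysis. No new visits, specimens or data are needed.

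### The only longitudinal steatosis–fibrosis analysis correlates change with change, so it can show nothing, or the wrong sign, if the level of steatosis drives fibrosis; add a lagged level analysis beside it

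*Combined protocol and SAP*

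**What the plan says.** Specific Aims opens with the hypothesis: "The central hypothesis of this ancillary study is that hepatic steatosis plays a key role in the development of fibrosis and cirrhosis". Background and Significance frames the exposure as the frequent presence of steatosis, and says of the longitudinal part: "It will also determine if changes in hepatic steatosis correlate with changes in hepatic fibrosis further supporting a role of hepatic steatosis in fibrogenesis".

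The Longitudinal study list under Data Analyses has five items:

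- Items 1 and 2 describe the prevalence of steatosis and its change, overall and by arm.
- Item 3 is "Correlation between changes in hepatic steatosis with changes in hepatic fibrosis".
- Item 4 relates change in steatosis to change in its own risk factors.
- Item 5 concerns insulin resistance.

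Only item 3 links steatosis to fibrosis. It names no interval, coefficient, covariates or treatment term. Steatosis level is set against fibrosis (Ishak score and morphometry) only under the Cross-sectional study heading.

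Steatosis has five ordinal grades, 0 to 4+. Materials and Methods says: "All patients will have repeat liver biopsies at the end of years 2 and 4". Fibrosis and steatosis are assessed on the baseline, M24 and M48 biopsies.

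**The concern.** The hypothesis is mainly about level: a fatty liver develops more fibrosis. Item 3 uses change in steatosis as the exposure. Someone graded 4+ at all three biopsies and someone graded 0 at all three have the same exposure value, so the most informative contrast drops out. No listed analysis asks whether baseline or year-2 steatosis predicts later fibrosis progression. Serial biopsies allow exposure to be measured before outcome, and the plan does not use that.

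At stake is how a null or negative item 3 would be interpreted. Data Analyses expresses confidence that a correlation will be shown if there is one, and Pitfalls and Limitations expects a fibrosis-promoting factor to show up easily in these patients. Beside those statements, a flat item 3 could be taken as evidence on the main question when the analysis was not able to answer it.

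**Working it through.** The plan gives no power, alpha or effect size for item 3, so there is no figure to reproduce. Its only numerical support is the comparison with a 148-patient study: 3 × 148 = 444 and 4 × 148 = 592.

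**Assumptions, not from the documents.** Two-sided alpha 0.05; grade shares 20/30/30/15/5%; two-year correlation of latent steatosis 0.5 to 0.9; true effect r = 0.25 on fibrosis change; 1000 runs per setting.

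**Algebra.** Let S0 and S4 be steatosis at baseline and year 4, dF the change in fibrosis, and e noise unrelated to steatosis.

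1. *Average level drives progression.* With dF = b(S0 + S4)/2 + e,
 Cov(S4 − S0, dF) = (b/2)(Var S4 − Var S0).
 This is zero when the spread of steatosis is stable, whatever the size of b.
2. *Baseline level drives progression.* With dF = b·S0 + e, corr(S0, dF) = r, equal variances, and ρ the correlation of S0 with S4,
 corr(S4 − S0, dF) = −r·√((1 − ρ)/2).
 Two-year correlations of 0.5, 0.7 and 0.9 give ρ = 0.25, 0.49 and 0.81. With r = 0.25 the results are −0.25·√0.375 = −0.153, −0.25·√0.255 = −0.126 and −0.25·√0.095 = −0.077.

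**Simulation with five grades and integer fibrosis change, N = 444 to 592.**

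| What drives fibrosis change | Item 3: mean r | Item 3: significant | Baseline steatosis as predictor |
|---|---|---|---|
| Average level | about 0.00 | 4% to 6% | mean r 0.18 to 0.23, significant in 97% to 100% |
| Baseline level | −0.15 to −0.08 | 42% to 97%, all negative | mean r about 0.24, significant in at least 99.9% |
| Change in steatosis | about 0.24 | at least 99.9% | mean r −0.15 to −0.08, significant in 44% to 96%, negative |

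**If the spread is not stable** (average of the three biopsies drives progression, N = 444, two-year correlation 0.7). If steatosis falls and its spread shrinks by 20%, item 3 averages −0.06. If the spread grows by 20%, it averages +0.03 and is significantly positive in 8% of runs.

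**Sample size does not help.** By Fisher's z, the smallest correlation detectable with 80% power is tanh((1.96 + 0.84)/√(N − 3)): 0.133 at N = 444 and 0.115 at N = 592. More patients cannot reveal a correlation whose expected value is zero.

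**A fourth model: the later level drives progression** (n = 500, 0.2 SD per grade, baseline-to-year-4 latent correlation 0.4/0.6/0.8). Item 3 is significant in 78%/62%/40% of runs and baseline steatosis in 39%/73%/94%. Neither analysis is better throughout.

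**Power of the added analysis in smaller sets.** The longitudinal part is limited to completers: "This study will include all patients who completed the trial and have repeat liver biopsies at the end of years 2 and 4". Their number is not given. Under the average-level model with 0.2 SD per grade, baseline steatosis has 67% to 90% power with 300 completers. It has about 55% to 71% with 250 and Ishak capped at 6 (assumed baseline mix 30/30/20/20% for scores 3 to 6). With 0.1 SD per grade and n = 500 it has 36% to 59%.

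**The case against.** The strongest defence is that item 3 answers a question the plan does ask. Specific Aims also proposes that interferon works partly by reducing steatosis. That is a claim about change, and item 3 suits it. If change drives fibrosis, item 3 succeeds and baseline steatosis points the wrong way. This stands, and it is the reason to keep item 3.

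A reader might infer four stronger things, which the documents do not support:

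- *That item 3 is blind to any level effect.* It is blind when average level drives progression and the spread is stable. When the later level drives progression it has moderate power. The documents do not say which model holds.
- *That a persistent 4+ patient who progresses counts against the hypothesis.* With mean steatosis change near zero, that patient contributes about nothing to the correlation. The patient is uninformative, not contrary.
- *That the plan ignores steatosis level.* Aim 2 asks for a correlation, and the cross-sectional analyses test it by level. What they lack is time order.
- *That the sponsor will read a null as refutation, so item 3 must give way to a new primary analysis.* No passage says so; Background and Significance presents item 3 as further support. The plan ranks no analysis as primary, and demoting item 3 would be a debatable trade.

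Item 3 also states no interval. Concurrent change is the natural reading because no lag is described, but it is an inference.

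**Conclusion.** The concern holds as a gap in the analysis list. The plan has no longitudinal analysis of steatosis level against later fibrosis, and item 3 cannot stand in for one. If level drives progression, item 3 can show zero correlation (average level, stable spread) or a negative one (baseline level) although the central hypothesis is true.

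The two sign results follow from the algebra under those models. Every percentage rests on assumed effect sizes, grade shares and autocorrelation, and the 97% to 100% figures use numbers close to entry, not completers. The documents do not support calling item 3 invalid or replacing it. This is a should-fix: one complementary analysis is missing on the study's own central question.

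**What to change.** Keep item 3, state its interval, and tie it to the hypothesis that interferon's benefit runs partly through reduced steatosis. Add beside it a prespecified lagged analysis:

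- **Exposure:** baseline steatosis grade, and year-2 grade for the year 2 to year 4 interval.
- **Outcome:** subsequent change in Ishak score and in morphometric fibrosis.
- **Adjustment:** fibrosis at baseline, randomized arm, BMI, alcohol and diabetes.
- **Ceiling:** patients starting at Ishak 6 cannot rise on that scale, so use morphometry for them or restrict the Ishak analysis to those who can progress.

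State that a null in item 3 alone does not refute a role of steatosis. Note that the baseline biopsy precedes six months of combination therapy, so the baseline grade is an imperfect exposure for the randomized period; the year-2 grade helps there.

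The cost is plan wording and one more analysis. No new data are needed. Power will be below the figures for 444 to 592 patients, so give the expected number of completers with repeat biopsies and the effect that number can detect.
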